13.3 Stratification Factors

Randomization will be stratified by enrolling hospital and unilateral vs bilateral mastectomy following a permuted block randomization supplied by the statistician.

13.4 Interim Monitoring Plan

Data and safety monitoring is described in section 12.

13.5 Analysis of Primary Endpoints

All randomized patients will be included in all analyses. Minimal missing data is expected; therefore, in the event of missing data, no imputation will be performed. The analyzable sample for the primary endpoint includes participants who are randomized and have reported a pain score at T3 regardless of intervention use. The primary endpoint is pain intensity measured on the 0-10 scale at the follow-up clinic appointment (T3). The pain score will be summarized at each time point and plotted. The T3 pain score will be compared between UC and Jacki groups using a Wilcoxon rank sum test. Due to the nature of the pain measure (i.e., integers on a 0-10 scale), there will be ties in pain score, and the number of ties could affect the performance of the non-parametric test.

Depending on the structure of the data, a t-test may be considered with a possible transformation. Assumptions will be examined and a method selected prior to testing.

Additionally an analysis of covariance (ANCOVA) approach may be considered. Factors that may be associated with the T3 pain score (baseline score, time since discharge, unilateral vs bilateral mastectomy, number of post-surgical drains, neoadjuvant chemotherapy, axillary lymph node dissection, pain management at home with pain medication, and post mastectomy clothing) will be assessed univariately and then adjusted in a multivariable model. The change in pain over time will also be evaluated using linear mixed models.

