5.8 Criteria for Taking a Participant Off Study

Participants will be removed from study when any of the following criteria apply:

- Lost to follow-up
- Withdrawal of consent for data submission
- Death
- It is considered to be in the participant's best interest
- The study device or procedures are found to be unsafe or ineffective
- There is any problem with using the study device or following study procedures
- The participant's condition worsens
- A decision is made to close the study
- Or for any other unforeseen reasons that make it necessary to stop the participant's participation in the research study

The reason for taking a participant off study, and the date the participant was removed, must be documented in the case report form (CRF).

For Centralized Subject Registrations, the research team submits a completed Off Treatment/Off Study form to ODQ when a participant comes off study. This form can be found on the ODQ website or obtained from the ODQ registration staff.

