13.2 Sample Size, Accrual Rate and Study Duration

The primary objective of this study will be to compare pain intensity (measured on the 0-10 scale, PINS) at the follow-up clinic appointment when all drains are removed (T3) between those randomized to UC or Jacki groups. A reduction of 1.0 on the PINS is thought to be clinically significant. With a sample size of 130 there is 80% power to detect a 1-point difference in PINS between UC and Jacki groups using a Wilcoxon rank sum test at the 2-sided 0.1 significance level assuming a standard deviation of 2.2 from

the preliminary study. The following table depicts the impact on power if the standard deviation at the follow-up visits is smaller or larger than estimated.

Standard Deviation	Power
1.8	91%
2.0	86%
2.2	80%
2.4	74%
2.6	68%

With a projected 13% rate of attrition, a total of 149 participants enrolled will yield an analytic sample of 130 evaluable participants. This number of participants will be accrued and will complete data collection within 10 months, based on clinical volume .

Accrual Targets				
Ethnic Category	Sex/Gender			
	Females	Males	Total	
Hispanic or Latino	39	+ 0	=	39
Not Hispanic or Latino	91	+ 0	=	91
Ethnic Category: Total of all subjects	130	+ 0	=	130
Racial Category				
American Indian or Alaskan Native	0	+ 0	=	0
Asian	6	+ 0	=	6
Black or African American	13	+ 0	=	13
Native Hawaiian or other Pacific Islander	0	+ 0	=	0
White	111	+ 0	=	111
Racial Category: Total of all subjects	130	+ 0	=	130

No interim analyses are planned due to the short duration, minimal risk, and minimal burden of the study. There are no early stopping rules.

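### Section 13.5 bars imputation because little missing data is expected, while 13.2 plans for 13% attrition; T3 is not secured after removal, and no sensitivity analysis covers its absence

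*Combined protocol and SAP*

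**What the plan says.** Section 13.5 gives the missing-data rule for the primary endpoint: "Minimal missing data is expected; therefore, in the event of missing data, no imputation will be performed". The same paragraph states "All randomized patients will be included in all analyses" and then defines the set for the primary test as "participants who are randomized and have reported a pain score at T3 regardless of intervention use". It adds "The change in pain over time will also be evaluated using linear mixed models", but gives that model no T3 contrast and no missing-data role. ANCOVA is optional.

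Section 13.2 sizes the trial on 130 analysed participants and continues: "With a projected 13% rate of attrition, a total of 149 participants enrolled will yield an analytic sample of 130 evaluable participants". Attrition here therefore means having no T3 score that can enter the test.

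Section 5.8 lists the grounds for removing a participant from the study. They include "There is any problem with using the study device or following study procedures" and "The participant's condition worsens". The reason and date go on the case report form. The section does not say whether the T3 pain score is still sought, and section 5.7 on follow-up is marked not applicable.

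Section 5.1.3 offers a telephone or secure-file route for T3 within 24 hours when the form cannot be completed in clinic. It does not say that this covers participants already taken off study. Section 13.6 refers to the EORTC manuals for missing data, which covers only those instruments.

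**The concern.** The reason given for not imputing conflicts with the attrition that the plan itself projects. The two descriptions of who is analysed also cannot both hold once any T3 score is missing.

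The larger question is which scores will be missing. A problem with the device can arise only in the jacket arm, and section 7.1 lists pain and dislodged drains among the possible jacket events. Worsening can occur in either arm and may well be linked to pain. If removal ends data collection, a missing T3 score may depend on both arm and pain.

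A complete-case comparison is then no longer protected by randomization. It shifts toward the jacket if painful jacket problems end data collection, and toward usual care in the reverse case. The plan names no analysis that would show how far the T3 result depends on the absent scores.

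**Working it through.** **1. The plan's own figures.** Inputs from 13.2: 130 analysed (65 per arm, assuming 1:1), difference 1.0, SD 2.2, two-sided alpha 0.10, Wilcoxon test. Noether's formula:

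- p = Φ(1/(2.2√2)) = 0.626
- power = Φ(√(12 × 130 × 0.25) × (0.626 − 0.5) − 1.645) = 80.1%, against 80% stated

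For SD 1.8, 2.0, 2.4 and 2.6 the formula gives 91.5, 86.1, 74.0 and 68.1%, against 91, 86, 74 and 68%. The power table reproduces.

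Attrition: 149 × 0.87 = 129.6, and 149 − 130 = 19, or 19/149 = 12.8% without T3. The loss of numbers is already covered by enrolment, so the issue is bias and not power.

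**2. Bias under no true effect.** The documents do not say how much of the 13% is related to pain, so that share is varied. Assumptions:

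- 13% lost in each arm (about 10 people)
- usual-care loss random
- pain-related non-completers 1 to 3 points worse (the gap)

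The bias toward the jacket is 0.13 × share × gap. For example, 0.13 × 0.25 × 1 = 0.03, 0.13 × 0.5 × 3 = 0.20 and 0.13 × 1 × 3 = 0.39.

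**3. Error rates by simulation.** Settings:

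- 75 usual-care and 74 jacket participants
- normal scores with SD 2.2, rounded and clipped to 0–10, T3 mean 2.5, 3.5 or 5.0
- logistic pain-related loss calibrated to each share and gap, with random loss up to 13% in total
- tie-corrected Wilcoxon test at two-sided 0.10, 100,000 runs per cell

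False success is a significant result with an observed difference of at least 1.0 favouring the jacket, which is how 13.7.2 is read here.

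| Pain-related share of jacket-arm loss | Bias (points) | Type I error | False success |
|---|---|---|---|
| None (random) | 0 | 9.9–10.1% | 0.2–0.4% |
| Quarter (about 2–3 people) | 0.03–0.10 | 10.1–10.9% | 0.2–0.8% |
| Half (about 5) | 0.07–0.20 | 10.5–13.9% | 0.4–1.6% |
| All (about 10) | 0.13–0.39 | 11.8–26.3% | 0.6–4.7% |
| All, with half of usual-care loss also pain-related | 0.07–0.20 | 10.3–14.7% | 0.3–1.2% |

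If only usual-care loss is pain-related, the bias has the same size and runs against the jacket.

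**4. The same loss rule in both arms.** With no true effect, bias is within 0.003 and type I error is 9.9–10.1%. With a true 1-point benefit, the difference shrinks by 0.02 to 0.17 points and power is 73–80%, against 79–80% with random loss.

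**5. Tipping point.** The standard error is 2.2 × √(2/65) = 0.386. The significance threshold is about 1.645 × 0.386 × √(π/3) = 0.65 points. Suppose the trial observes a difference of 1.0 and usual-care loss is random:

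- 9.5 missing per arm: the missing fraction is 9.5/74.5 = 0.128. Significance is lost if missing jacket participants are about (1.0 − 0.65)/0.128 = 2.7 points worse than those observed.
- 14 missing in the jacket arm and 5 under usual care: 14/74.5 = 0.188, and (1.0 − 0.65)/0.188 = 1.9 points.

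**The case against.** The strongest reply has four parts.

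**The conflict may be one of wording.** The 13% is an enrolment allowance, and the missing data in 13.5 could mean gaps among participants who stay. Section 13.5 does not say so, however, and its analysis set drops everyone without a T3 score. Those are the participants 13.2 deducts, so this reading does not rescue the premise. The statement about all randomized patients is largely editorial, since the T3-reported set is defined explicitly just afterwards.

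**Safeguards exist.** Section 5.1.2 sets no floor on jacket use, non-users with a T3 score stay in the analysis, drain removal is part of routine care, and there is a remote T3 route. Chart review captures some pain documentation. These points have weight: stopping the jacket need not lead to removal. None of them, however, is stated to supply a T3 PINS score for someone taken off study.

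**The damaging scenario is extreme.** This stands. At mean 2.5 and gap 3, one calibration of the all-pain-related case loses about 57% of jacket participants scoring 6 and 90% of those scoring 8, against a flat 13% under usual care. Some loss may also precede discharge, when the jacket cannot be the cause. The quarter and half rows are the more useful guide, and the 1.0-point requirement in 13.7.2 limits false success.

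**The mixed model is already planned.** It can use T1 and diary scores and is valid if data are missing at random. But it is not specified as a check on the T3 contrast. Diaries are handed in at the follow-up visit, so a participant who misses it may have only T1.

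The consent pages were not available, so any wording there on data collection after removal could not be checked.

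**Conclusion.** The concern holds, as a point that should be fixed; confidence is medium. The premise of minimal missing data is at odds with the projected 13%. The removal and complete-case rules, followed as written, can bias the T3 contrast, and nothing in the plan would reveal it.

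The likely size is modest. If a quarter to a half of jacket-arm loss is pain-related and usual-care loss is random, the bias is 0.03 to 0.20 points against a 1.0-point target. The upper end of 0.39 points requires all jacket-arm loss to be strongly pain-related. These figures rest on assumed shares, gaps and equal 13% loss per arm. The observed data cannot identify the true mechanism. Lack of imputation is not in itself an error: loss unrelated to pain causes no bias.

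**What to change.** 1. **Section 5.8.** Separate stopping the jacket or study procedures from ending data collection. State that the T3 PINS score, in clinic or by the existing remote route, and the diary are still sought after removal. Exceptions are death, loss to follow-up, withdrawal of consent for data, study closure, or contact judged against the participant's interest. This concerns data collection only and leaves clinical care unchanged.
2. **Section 13.5.** Keep the Wilcoxon test on reported T3 scores as primary and limit the no-imputation rule to that test. Delete the premise, reword the all-randomized statement to match the T3-reported set, and report missing T3 scores and the recorded reasons by arm.
3. **One sensitivity analysis of the T3 contrast.** Name in advance either the planned mixed model or multiple imputation, using T1, returned diary scores, arm and strata, and add a delta-adjusted tipping point.

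The cost is wording in two sections, one extra analysis and a little more follow-up contact. The sample size does not change, and removal reasons are already recorded. The mixed model or imputation assumes missing at random and adds little where only T1 is available. Most of the value therefore lies in retrieving T3, which cannot be done later, and in the tipping point.

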2.5 Preliminary Data

A preliminary survey study was conducted to explore self-reported pain intensity levels (just before discharge to ambulatory care) in patients post mastectomy in the Boston area. The sample (n=88) had a nearly equal distribution of age above and below 50 years; most were college educated and married/partnered. Of the 88 participants, 39% reported moderate to severe pain intensity, 53% reported pain several times a week to constantly, and 34% reported pain intensity as fair to almost unbearable soon after surgery. Sixty percent of participants had received a bilateral mastectomy, and 43% of these had bilateral implant reconstruction. Mean scores on the 0-10 pain intensity scale were 5.26 (SD=2.28) for those who had bilateral mastectomy and 2.5 (SD=2.13) for those having single mastectomy; participants who had reconstruction at the time of surgery pain averaged 4.98 (SD=2.18).

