5. TREATMENT AND/OR IMAGING PLAN

5.1 Treatment Regimen

5.1.1 Enrolling Sites and Study Entry

A sample of 130 women who have had or will have mastectomy with reconstruction will be recruited.

Screening will be conducted by a research team member using the clinical surgery and post-op schedule to identify eligible patients. A clinical care nurse or clinical research associate who is a member of the research study team will invite the participant to hear about the study, and if the patient agrees to participate, will consent the participant. The research team member will complete the eligibility checklist.

The research team member will fax the consent form and eligibility checklist to the Office of Data Quality to register the participant and will receive the participant's randomized study group assignment. Participants will be randomly assigned in blocks of random permuted size, stratified by site and unilateral vs bilateral mastectomy, to the usual care pain management (UC) or "Jacki" plus usual care (Jacki) groups.

The research team member will meet the participant in the hospital on the first day post-surgery (or second day, if the patient is too sick, has a surgical complication, or is in too much pain or distress to be approached the first day) to collect the baseline (T1) questionnaire and will provide the post-discharge daily diary questionnaires (T2) to the participant, answer questions, and make arrangements for collection of the follow-up questionnaire (T3) with the participant at the clinic visit when all the post-surgical drains are removed. The research team member will telephone or email the participant at home the first or second day after discharge to remind her to fill out the T2 daily questionnaire; if the participant has multiple follow-up visits before all drains are removed, the research team member may also telephone, email or meet the participant at follow-up visits to remind her to continue filling out the T2 daily questionnaire until all drains are removed.

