5.1.2 Treatment Regimen

A clinical care nurse will provide instruction to participants allocated to the Jacki arm on safe and appropriate use of the Jacki (for example, how to put on the jacket and tuck drainage tubes into jacket pockets, and the need to remove drainage tubes from jacket pockets prior to removing the jacket). Participants in the Jacki arm will be encouraged to use the jacket at home between discharge and their follow-up clinic appointment; no minimum amount of use is required.

Participants in both groups will receive all usual pain management including prescription of pain medications and instructions on pain management post-discharge as standard of care.

The treatment period for participants in both arms is from discharge from the hospital post mastectomy until the follow-up clinic appointment at which all drains are removed, usually in 7-14 days, sometimes as long as 28 or (rarely) 42 days.

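### Randomisation is stratified by hospital and laterality, but the primary Wilcoxon test uses neither factor nor T1 pain, and no single adjusted analysis is prespecified

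*Combined protocol and SAP*

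**What the plan says.** Section 13.3 states: "Randomization will be stratified by enrolling hospital and unilateral vs bilateral mastectomy following a permuted block randomization supplied by the statistician". Section 5.1.1 says the same.

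The primary comparison in section 13.5 is a plain two-group rank test: "The T3 pain score will be compared between UC and Jacki groups using a Wilcoxon rank sum test". Section 13.2 sizes the trial for that test, "using a Wilcoxon rank sum test at the 2-sided 0.1 significance level assuming a standard deviation of 2.2", with 130 analysed participants and a 1-point difference.

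Section 13.5 also allows a t-test, possibly on transformed data, with the method to be chosen after assumptions are examined but before testing. It then offers ANCOVA as a further possibility. The candidate factors include the baseline score and laterality, but not hospital. They also include home pain medication, post mastectomy clothing and time since discharge.

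The only pain data by laterality are in section 2.5, from a survey to "explore self-reported pain intensity levels (just before discharge to ambulatory care) in patients post mastectomy". Mean scores were "5.26 (SD=2.28) for those who had bilateral mastectomy and 2.5 (SD=2.13) for those having single mastectomy". Patients with reconstruction at the time of surgery had mean 4.98 and SD 2.18. The primary endpoint comes later: drains are out "usually in 7-14 days, sometimes as long as 28 or (rarely) 42 days" after discharge (section 5.1.2).

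**The concern.** Blocking within strata balances the arms on hospital and laterality. If laterality still affects pain at T3, an analysis that ignores it leaves the between-stratum variation in the error term. The test then rejects less often than its nominal level under the null and has less power than a stratified test. The T1 score is collected for everyone and could reduce the error further.

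The optional ANCOVA does not settle this. It is not committed to, it omits a randomisation factor, and its covariates are screened rather than fixed. Home medication and clothing are recorded after discharge, and time since discharge at T3 is set by the date of drain removal. Section 2.4 describes the Jacki itself as a garment for use after mastectomy, so adjusting for clothing can remove part of the treatment effect.

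The choice between a Wilcoxon test and a possibly transformed t-test has no decision rule, and the plan does not say that the assumption check is blind to arm. At stake are precision that could be had at almost no cost, and certainty about which analysis is primary.

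**Working it through.** **Inputs from the documents.** Two-sided alpha 0.10, N = 130, difference 1.0 and SD 2.2 (section 13.2). Laterality means 5.26 and 2.5, 60% bilateral in the survey, and reconstruction-group mean 4.98 with SD 2.18 (section 2.5).

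**Assumed.** 1:1 allocation, a T3 laterality gap from 0 to 2.76, a T1–T3 correlation from 0 to 0.6, and three hospitals with no hospital effect.

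**Step 1: reproduce the plan's power.** Noether's formula for a normal shift is power = Φ(√(3N)·|p − 0.5| − 1.645), with p = Φ(δ/(SD·√2)). At SD 2.2, p = Φ(1/3.111) = 0.626, and √390 × 0.126 − 1.645 = 0.845, so power is 80.1%. For SD 1.8/2.0/2.2/2.4/2.6 the formula gives 91.5/86.1/80.1/74.0/68.1%, against the plan's 91/86/80/74/68%. The plan's figures are therefore for an unstratified Wilcoxon test. SD 2.18 gives 80.7%.

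**Step 2: laterality gap and mix.** The pre-discharge gap is 5.26 − 2.5 = 2.76. If those means carry over to reconstruction patients, the bilateral share is (4.98 − 2.5)/2.76 = 0.90.

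**Step 3: variance due to laterality.** Between-stratum variance is q(1 − q)·gap². With a within-stratum SD of 2.2 (variance 4.84):

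- 90% bilateral, full gap: 0.09 × 7.618 = 0.686; overall SD √5.526 = 2.35 (12% of variance between strata)
- 90%, half gap (1.38): overall SD 2.24 (3%)
- 60%, full gap: 0.24 × 7.618 = 1.828; overall SD √6.668 = 2.58 (27%)
- 60%, half gap: overall SD 2.30 (9%)

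**Step 4: unstratified Wilcoxon against van Elteren by laterality.** Each cell is 8,000 simulated trials with permuted blocks of 2, 4 or 6 within laterality and hospital. Ranges span continuous and 0–10 integer scores, with tie-corrected variance. Simulation error is 0.4–0.5 points for power and about 0.3 points for type I error.

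| SD held at | Bilateral | T3 gap | Power, unstratified | Power, van Elteren | Type I error, unstratified |
|---|---|---|---|---|---|
| overall 2.18 | 90% | 2.76 | 83–84% | 86–87% | 0.08 |
| overall 2.18 | 90% | 1.38 | 81–82% | 81–83% | 0.09–0.10 |
| overall 2.18 | 90% | 0 | about 81% | about 81% | nominal |
| within 2.2 | 90% | 2.76 | 77–78% | 80% | 0.080–0.086 |
| within 2.2 | 90% | 1.38 | 79–80% | 80–81% | about 0.10 |
| within 2.2 | 60% | 2.76 | 71% | 80–81% | 0.055 |
| within 2.2 | 60% | 1.38 | 78–79% | 80–81% | 0.080–0.085 |

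With no gap, the two tests differ by less than 1 point. Repeat simulations of the 60%, full-gap case gave 71–73% unstratified against 80–82% stratified.

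**Step 5: ANCOVA with T1 pain.** At within-stratum SD 2.2, 90% bilateral and half the gap, simulated power is 81–82% at correlation 0, 83% at 0.2, 86–88% at 0.4 and 93–94% at 0.6. The unstratified test has 79–80%. As an analytic check for T1 alone at correlation 0.4, the residual SD is 2.2 × √(1 − 0.16) = 2.016. Then 1/(2.016 × √(2/65)) − 1.645 = 1.18, which is 88% power.

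**The case against.** An unadjusted rank test after stratified randomisation is valid. It is the test the trial was powered on, and it needs only the T3 score. The strongest arguments against the concern are these.

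- **Small likely loss.** This stands: 0–3 points is minor. Adding three assumed hospitals to a van Elteren test costs about 1 point, so with no gap it would be slightly worse than the plain test.
- **The scenarios do not fit section 2.5 perfectly.** This also stands. A 90/10 mix with the reported SDs gives √(0.9 × 5.198 + 0.1 × 4.537 + 0.686) = 2.41, not 2.18. Holding 2.18 implies a within-stratum SD of √(4.752 − 0.686) = 2.02, below both reported values. The 10-point case uses the mix of a general mastectomy sample. The figures are a range, not a forecast.
- **The T1 gain rests on an undocumented correlation.** True. At zero correlation the 81–82% owes nothing to T1.
- **T1 may follow knowledge of arm, and may be missing.** Section 5.1.1 places assignment at registration and does not give the order relative to T1. Participants may skip questions and nothing is imputed. Both need a sentence in the plan, but neither argues for ignoring the strata.
- **The success rule limits the gain.** Section 13.7.2 asks for a significant difference of at least 1.0. Significance alone needs about 1.645 × 2.2 × √(2/65) = 0.63 points, so on a literal reading the 1.0 threshold binds. With a true 1-point effect, the chance of meeting both conditions is then 45–50% with Wilcoxon and 49–52% with ANCOVA. That is a separate problem with the rule. It limits the benefit only on that reading, and the estimate still gains precision.
- **The post-randomisation covariates sit only in a supplementary model.** Correct, and they do not affect the Wilcoxon test. They do mean that the listed ANCOVA cannot serve as the adjusted analysis without change.

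**Conclusion.** The concern holds. The primary test ignores both randomisation factors and the T1 score, and the only adjusted analysis is optional and poorly specified. This is a matter of efficiency and prespecification: the test is valid and at worst conservative. If the overall SD at T3 is 2.18, the unstratified test still meets 80%.

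The loss from ignoring laterality is likely 0–3 points of power, with about 10 as the extreme. T1 adjustment may be the larger source of gain, from almost nothing at zero correlation to more than 10 points at 0.6. Confidence in the size is moderate, because the T3 gap, the bilateral share, the T1–T3 correlation and the number of hospitals are not in the documents. The change should be made, but the trial does not fail without it.

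**What to change.** - Name one primary analysis in section 13.5: ANCOVA of T3 pain on arm, T1 pain, laterality and hospital (main effects), reporting the adjusted difference with a 90% confidence interval. If a rank test is preferred, use a van Elteren test stratified by the randomisation factors.
- Keep the unstratified Wilcoxon test as a sensitivity analysis.
- Exclude home pain medication, post mastectomy clothing and time since discharge from the primary model.
- Remove the open choice between a Wilcoxon test and a transformed t-test, or make the assumption check blind to arm with a written decision rule.
- If T1 pain is a covariate, state that it is completed before the participant learns her arm, and say how a missing T1 score is handled so that T3 scores are not dropped.

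The cost is SAP wording, because T1 pain and both strata are already collected. ANCOVA spends a few degrees of freedom on hospital. A van Elteren test by both factors gives about 1 point less power than by laterality alone, assuming three hospitals.
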